Participants will be healthy young men and women (N=80, 80). They will first participate two fMRI scans, when they receive oral MA (20 mg) and PL, in random order under double blind conditions. During the scan they will complete the Monetary Incentive Delay task (MID) (Knutson, Adams et al. 2001) and the Doors task (Carlson et al. 2011) and resting state data will be obtained. The primary outcome measures during these sessions will be task-related (anticipation and receipt of reward) regional brain activation, task-related connectivity, and resting state functional connectivity. After the two scans, subjects will participate in two behavioral sessions during which they receive MA (20 mg oral) or PL in mixed order, in color-coded capsules. Subjects will complete mood and drug effects questionnaires, and cognitive tasks.

**Subjects.** Healthy men and women aged 18-35 years will be recruited from the university and surrounding community without regard to race or ethnicity, according to Protocol 13681B. Initial

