**Imaging data analysis.** Imaging data from fMRI tasks will be preprocessed and analyzed using AFNI tools, as in Van Hedger (Van Hedger, Keedy et al. 2018). Preprocessing steps include alignment of each time series, spatial registration of the aligned time series to the anatomical scan, anatomical scan warped to standard space and warp applied to functional data, functional data spatially smoothed, and intensity normalization. Neural activation for conditions of interest from each task will be estimated using AFNI's 3dDeconvolve program, incorporating motion and heart rate/respiration as regressors. For MID, we will use a gamma response function to create activation maps for each task element: cues, motor response, and feedback. For the secondary tasks, we will use block functions and create contrast maps between the two block types. Mean activation for each subject at each scan session will be extracted from regions of interest (ROI). For MID, ROIs will be 8mm spheres created around coordinates reported in a recent meta-analysis of 50 MID fMRI studies (Oldham, Murawski et al. 2018). For Cue: caudate, putamen ventral striatum, thalamus, and anterior insula; Feedback: ventromedial prefrontal, orbitofrontal cortex, ventral striatum, amygdala, and will be a subtraction of mean activation of loss trials from win trials in each ROI (this contrast is the most common and more sensitive approach, per Oldham); Motor: all prior ROIs (to confirm lack of drug effect), primary sensorimotor cortex. ROI activation will be a subtraction of mean activation of loss trials from win trials in each ROI (this contrast is the most common and more sensitive approach, per Oldham). We will also look specifically at win vs neutral and loss vs neutral to confirm whether findings are driven by sensitivity to reward or avoiding loss. Tapping: primary motor cortex: dorsal striatum (caudate, putamen). For connectivity analyses of the MID task and of resting state, we will use the CONN toolbox (Whitfield-Gabrieli and Nieto-Castanon 2012) which employs similar preprocessing steps (alignment and spatial standardization, intensity normalization, motion estimation, white matter and CSF-based regressors) implemented through SPM12. We will use a 2mm displacement cutoff. For MID task-related connectivity, we will conduct an ROI-to-ROI analysis, using the spherical masks described previously. The toolbox allows comparison of correlation strengths (Pearson r converted to Fisher z) of the timeseries between each pairing of the ROIs. We will compare these correlations between drug and placebo sessions, as well as extract ROI-to-ROI correlation values for assessment in relation to behavioral measures. For resting state, we will calculate seed-based connectivity maps separately for MA and placebo, as per our prior study (Weafer, Van Hedger et al. 2019). Seeds will be bilateral caudate, putamen, and ventral striatum. We will conduct paired t tests within CONN to compare connectivity following MA and placebo. As our hypotheses are specific to frontal and subcortical reward circuitry, statistical inferences will be made within an anatomically-focused frontal-insular-striatal partial brain mask. The mask will include medial and lateral frontal and orbital regions, bilateral precentral gyri, anterior and middle cingulate cortex, anterior insula and ventral striatum. Drug order will be included as a covariate in all analyses.

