## **C6. Statistical Plan**

**Aim 1 is designed to determine the effects of MA on regional brain activity during anticipation of reward, as well as changes in connectivity both during the task and at resting state.** We hypothesize MA will increase activation in mesolimbic reward regions during the task and increase both task-related and resting state functional connectivity in reward circuitry. For task-related activation we will use SPSS to conduct, for each MID task component separately (cue, motor response, feedback), within-group contrasts of the MA vs PL sessions using the extracted activation from the ROIs. Based

on our preliminary data, we expect greater activation in ROIs, specifically dorsal and ventral striatal reward regions (i.e., caudate, putamen, and nucleus accumbens) following MA compared to PL for cue and feedback. Given that we did not see any effect of methamphetamine on motor cortex in our preliminary data, we do not expect to see a drug effect on motor here. Secondary, exploratory whole brain analyses will also be conducted comparing MA vs PL in each task component. To examine the effects on task-related connectivity, we will use the CONN toolbox to conduct within-group ROI-to-ROI contrasts, e.g., we will compare correlation strengths of the seed regions to one another during the MA vs. the PL scan, and expect stronger connectivity (correlation) from the MA session, specifically between striatal (i.e., caudate, putamen, and nucleus accumbens) and medial frontal (i.e., ventromedial prefrontal and orbitofrontal cortex) reward regions. To assess resting state connectivity drug effects, we will use CONN to contrast the seed-based connectivity maps from the MA vs PL sessions. CONN analyses will be evaluated at  $p < .05$ , familywise, within the fronto-insular-striatal mask. Based on our preliminary findings (Weafer, Van Hedger et al. 2019), we hypothesize greater connectivity between striatal seed regions and medial frontal reward regions (i.e., ventromedial and orbitofrontal cortex). All analyses will include drug order, age, and sex as covariates.

Power analysis for Aim 1: Our preliminary data indicate a large effect size for the effect of MA compared to placebo on resting state fronto-striatal (NAcc to OFC) functional connectivity ( $d = 0.94$ ). The proposed sample of  $N=160$  would provide over 99% power ( $\alpha = .05$ ) to detect an effect of MA on resting state functional connectivity.

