Power analysis for Aim 2: For correlational analyses, the proposed sample size of  $N=160$  yields power over 80% to detect correlations of 0.22 and greater for a two-tailed  $\alpha=.05$  test. This corresponds to a small to medium effect size (Cohen's  $f^2 = .051$ ), and so the sample size will allow us to detect reasonable associations with good statistical power.

Ancillary analyses. The design includes several ancillary measures that will serve as important controls. During the fMRI scan, subjects will complete a simple motor task and we will examine neural responses to this task, in both reward-related and other brain areas. During the MID task, we will collect data during receipt of reward, as well as our primary measure of anticipation of reward. On the behavioral sessions, subjects will also complete cognitive tasks (Stop Task, Go No Go and Simple Reaction time), a simple motor task, and two reward-learning tasks. Cardiovascular measures will be obtained during the drug and MA sessions. These measures will allow us to investigate

individual differences in neural function (as determined by the scan) and behavioral measures, both without drug (PL session) and after drug. We will examine the specificity of any observed correlations to reward-related tasks. We will also assess MA vs PL changes identified in fMRI data against changes noted in the ASL data.

Sex differences. We will compare each of the measures in men and women (N=80, 80), and if sex differences are detected they will be included as covariates in the correlational analyses. We do not expect significant sex differences especially because women will be tested during the follicular phase of the cycle (White, Justice et al. 2002) and (Wilkinson, Khan et al. 2009). Nevertheless, we believe it is important to investigate drug responses in men and women, with sufficient statistical power.

Alsop, D. C., J. A. Detre, et al. (2015). "Recommended implementation of arterial spin-labeled perfusion MRI for clinical applications: A consensus of the ISMRM perfusion study group and the European consortium for ASL in dementia." Magn Reson Med **73**(1): 102-16.

Ballard, M. E., J. Weafer, et al. (2015). "Effects of Acute Methamphetamine on Emotional Memory Formation in Humans: Encoding vs Consolidation." PLoS ONE **10**(2): e0117062.

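### The MID motor component is meant to establish that MA has no effect there, but the only planned analysis is a difference test, which cannot establish absence

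*Combined protocol and SAP*

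**What the plan says.** The combined protocol and SAP treats the MID motor-response component in four places.

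- **Imaging data analysis** gives its regions and purpose: "Motor: all prior ROIs (to confirm lack of drug effect), primary sensorimotor cortex". The purpose is attached to the reward ROIs; sensorimotor cortex is listed after them.
- **C6, Aim 1** gives its analysis: "for each MID task component separately (cue, motor response, feedback), within-group contrasts of the MA vs PL sessions", on activation extracted from the ROIs. This is a difference test, identical for all three components.
- **C6, Aim 1** states the expectation: "we do not expect to see a drug effect on motor here". The reason given is that preliminary data showed no effect in motor cortex. No estimate or interval is quoted.
- **C6, Ancillary analyses** describes the wider role of such measures: "The design includes several ancillary measures that will serve as important controls".

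The design is a paired crossover: "Participants will be healthy young men and women (N=80, 80"), scanned twice, "when they receive oral MA (20 mg) and PL, in random order under double blind conditions". The two power statements concern power "to detect an effect of MA on resting state functional connectivity" (d = 0.94) and power "to detect correlations of 0.22 and greater for a two-tailed" test. Neither concerns a conclusion of no effect.

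**The concern.** The stated purpose is to establish a null, and the stated tool is built to reject one. The plan does not spell out how the result will be read. With no other rule given, the natural reading is that a non-significant motor contrast counts as confirmation. Such a result is also what a real but modest effect, a reduced sample or noisy scans would produce, so poorer data make the control easier to pass.

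At stake is one strand of the argument that MA acts on reward processing rather than on the BOLD response generally. A paper could report the motor null as demonstrated when the data only failed to reject it.

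The measure itself is also unclear. Directly after the motor list, Imaging data analysis defines ROI activation as win trials minus loss trials, while the MID task description says that cue conditions are collapsed for primary analyses. If win minus loss applies to the motor component, a null would concern that contrast and not the motor response.

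**Working it through.** **Inputs.** 160 pairs (Methods; C6). Alpha .05 (C6, Aim 1; sidedness not stated there, two-sided assumed). The documents give no margin, no SD of the MA minus placebo motor difference and no dropout rate. Effects are therefore in SDs of the paired difference (d), and margins and losses are illustrative. Covariates are ignored; they cost a few degrees of freedom.

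**1. The plan's own figures.**
- Aim 1: d√n = 0.94 × √160 = 0.94 × 12.65 = 11.9, so power is essentially 100%. The plan says over 99%.
- Aim 2: atanh(0.22) × √157 = 0.2237 × 12.53 = 2.80; Φ(2.80 − 1.96) = 80%. The plan says over 80%.

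Both reproduce. Neither bears on the motor null.

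**2. What the planned difference test would miss.** Paired t test, noncentrality d√n:

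| True d | Power, 160 pairs | Missed, 160 pairs | Missed, 136 pairs (15% loss) |
|---|---|---|---|
| 0.10 | 24% | 76% | 79% |
| 0.15 | 47% | 53% | 59% |
| 0.20 | 71% | 29% | 36% |

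Power reaches 80% only at d = 0.22. Noise acts through d: if the SD of the change rises by a third, a fixed raw effect worth 0.20 becomes 0.20 ÷ 1.333 = 0.15, and the miss rate at 160 pairs goes from 29% to 53%.

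**3. What an interval rule could deliver at N = 160.** The 90% CI half-width is t(.95, 159)/√160 = 1.654/12.65 = 0.131 SD. Power to show equivalence when the true difference is zero is approximately 2Φ(m√n − 1.645) − 1:
- m = 0.20: 2Φ(0.885) − 1 = 62%
- m = 0.25: 2Φ(1.517) − 1 = 87%
- m = 0.30: 2Φ(2.150) − 1 = 97%

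Exact integration over the sample SD gives the same rounded values. If the true d is 0.10, power is 59% at 0.25 and 81% at 0.30. With 136 pairs and a true zero, it is 79% and 93%.

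**4. Several ROIs.** The text yields nine regions: caudate, putamen, ventral striatum, thalamus, anterior insula, ventromedial prefrontal, orbitofrontal, amygdala and sensorimotor cortex. If all nine must pass and are treated as independent, power is 0.867⁹ = 28% at 0.25 and 0.967⁹ = 74% at 0.30. Positive correlation would raise these.

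**5. Why the margin should not be a multiple of the observed SD.** Take a fixed raw effect of 0.4, 160 pairs and a margin of 0.25 observed SD. The rule passes when the observed |d| is below 0.25 − 0.131 = 0.119. With SD 1, 2, 3 and 4, the true d is 0.40, 0.20, 0.133 and 0.10, and the pass rate is 0%, 15%, 43% and 59%. Noise makes such a rule easier to pass. With the margin fixed at 0.25 raw units, the pass rate is about 0% throughout.

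**The case against.** The strongest reply is that an equivalence rule changes few verdicts at full N. Significance requires an observed |d| above t(.975, 159)/√160 = 1.975/12.65 = 0.156, and the far 90% limit is then at least 0.156 + 0.131 = 0.287.
- At a margin of 0.30 SD, every non-significant result at 160 pairs would pass.
- At 0.25 SD, every significant result also fails equivalence. When the true effect is zero, only about 8% of verdicts change (95% non-significant against 87% passing).

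This stands, and it means that the choice of margin decides what the rule adds. It does not rescue the present wording: without a margin there is no statement of how large an effect was ruled out, and lost or noisy scans still favour a pass.

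A second reply is that the control is ancillary and not the only guard. This also stands. The plan has arterial spin labelling with conditional adjustment for blood flow, heart-rate and respiration regressors, cognitive tasks and a check of whether correlations are specific to reward tasks. A reader might infer that the reward-specificity claim rests on the motor null, or that a trivial significant motor effect would overturn it. The documents say neither.

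A reader might also extend the point to finger tapping. That task is described as informing on drug effects in motor regions, and no null is claimed for it.

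**Conclusion.** The concern holds for the MID motor-response component. The plan states a purpose of establishing no drug effect and supplies only a difference test, which at 160 pairs would miss a true d of 0.15 in 53% of trials and 0.20 in 29%. These figures assume a two-sided .05 test, one ROI and no losses.

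It is tempting to conclude that equivalence is simply affordable at N = 160. The documents do not support that without conditions, because they give neither a margin nor an SD. The 62%, 87% and 97% figures are per ROI, at a true difference of exactly zero, for margins that happen to equal 0.20, 0.25 and 0.30 SD. They fall if several ROIs must all pass or if a small effect exists.

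This is a minor point about an ancillary control. The primary Aim 1 test is untouched.

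**What to change.** Before unblinded analysis, add a short paragraph to C6, Aim 1 that does the following.

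1. Names the ROI or ROIs that carry the no-effect claim: the reward ROIs to which the stated purpose attaches, with primary sensorimotor cortex if intended. State whether all must pass.
2. Defines the motor measure as mean response over trials, not win minus loss.
3. Sets a numerical margin in fixed signal units, with its reason; for example, a stated fraction of placebo-session activation or of the expected cue effect. It should not be a multiple of the SD of the observed change.
4. Reports the MA minus placebo difference with its 90% CI, and uses the words *no relevant motor effect* only if the CI lies inside the margin.
5. If no margin can be justified, reports the CI and removes *confirm* from the imaging text.

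The cost is a few sentences and one interval per named ROI, on data already to be analysed; no extra participants or scans are needed. The downside is that a margin has to be defended, and the no-effect claim may then not be met.

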### ***Imaging tasks and data collection.***

***MID TASK:*** Following Knutson (Knutson, Adams et al. 2001), the MID task assesses neural responses for both reward anticipation and consumption, and offers actual small and large monetary gains and losses based upon performance. This optimized task version requires participants to respond rapidly during an individually determined response window. Response windows are titrated after a pre-scan practice and during imaging to ensure optimal performance, e.g., 50-80% success rates. There will be 2 runs consisting of 24 trials each. For each trial, a 500 ms anticipatory cue alerts the subject to the opportunity to either win money or avoid losing money, specified as +/- \$0.30 or \$3.00, or a neutral cue is given (\$0.0) indicating that no money is at stake. Win/avoid loss and \$0.30/\$3.00 are presented pseudorandomly and at equal frequency across 64 of the trials; 32 trials are the neutral cue condition interspersed with the other trials. After the cue there is a 2-4s (jittered) interval and then a stimulus (a white box) appears. The stimulus duration is derived from data collected during the pre-scan practice. Subjects are required to press their thumb button as quickly as possible while the stimulus is visible. Visual feedback is provided indicating whether the participant responded within the time frame. Pre-scan practice (PSP) assesses individual-specific reaction time (RT) for correct responses. PSP mean RT and standard deviation are used to calculate a response window for the stimulus cue during the first run of the MID inside the scanner. For example, a subject with a mean RT of 180ms and SD of 20 will have a stimulus duration/response window of 220ms (180+ 2\*20), and a delay jitter screen of 780ms (1000ms-220). The technician tracks performance after each run and uses the number of total correct responses to modify the response time for the next run. If a participant's accuracy falls below 50%, the stimulus duration/response window increases by 0.5 SD (and the delay jitter screen conversely). If the participant's accuracy exceeds 80%, then the stimulus duration/response window decreases by 0.5 SD. The subjects are told they will receive the money they win based on their performance, added to their payment for the scan. They cannot lose money, in accordance with the success rate calibration. The task takes ~20 minutes. For this study, cue conditions (receive/avoid losing \$0.30/\$3.00; or no

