money at stake) primarily enhance subject task engagement and will be collapsed for primary analyses, in accordance with limited clear knowledge of neural system differences distinguishing such conditions (Oldham, Murawski et al. 2018).

**Doors Task.** Participants will complete the doors task (Carlson et al. 2011) during BOLD fMRI to assess brain activation during monetary reward and loss. Briefly, two doors are presented on the screen, and participants are told that behind one of the doors is a monetary prize of \$.50 (signaled by '↑') and behind the other door is a loss of \$.25 (signaled by '↓'). For each trial, participants are instructed to use a button box to choose one of the two doors. They are told that they will either win or lose money based on their choices, and that they had a chance of winning between \$0 and \$15 total based on their performance. In actuality, the subjects' performance has no impact on outcomes. The task consists of 30 predetermined Wins and 30 Losses presented in a pseudorandom order over two runs. The task requires 15 minutes to complete, and all subjects earn \$10.

**Motor task:** Subjects will complete a motor task to provide information on the effect of the drug on activation of brain regions controlling motor function. As in an early study from our laboratory Uftring (Uftring, Wachtel et al. 2001), subjects will complete a finger tapping task in which they touch their right thumb and index finger together repeatedly for three 20s blocks, alternating with 4 20s rest blocks. We will assess for motor system changes during this task.

The scan will include a 10-minute resting state sequence, eyes open fixating on a light crosshair on a dark background, a high-resolution T1-weighted image for alignment and spatial standardization, and an Arterial Spin Labeling sequence to assess blood flow (described below).

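### Scored as win minus loss, the MID motor check cannot detect a methamphetamine effect on motor activation that is common to win and loss trials

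*Combined protocol and SAP*

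**What the plan says.** The plan is a combined protocol and SAP. Under imaging data analysis, the MID task is modelled in three elements: "we will use a gamma response function to create activation maps for each task element: cues, motor response, and feedback". The regions for the motor element are given as "Motor: all prior ROIs (to confirm lack of drug effect), primary sensorimotor cortex". The text runs straight on from the last of these regions to the scoring: "primary sensorimotor cortex. ROI activation will be a subtraction of mean activation of loss trials from win trials in each ROI". Feedback had already been given the same rule inside its own clause, so the later sentence reads as a general rule, and nothing in it excludes motor. Win versus neutral and loss versus neutral are added as follow-up contrasts.

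The MID task description states the motor demand for every trial alike: "Subjects are required to press their thumb button as quickly as possible while the stimulus is visible". It then says that the cue conditions "primarily enhance subject task engagement and will be collapsed for primary analyses", which is a different scoring rule.

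Section C6, Aim 1, compares MA with placebo (PL) on the extracted region values for each MID component, motor response included. Of the motor component it says: "we do not expect to see a drug effect on motor here".

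**The concern.** A motor control should be able to show a motor drug effect if there is one. Win and loss trials call for the same speeded thumb press. If MA raises or lowers the response to that press by the same amount on both, subtracting loss from win removes the effect before MA and PL are compared. The expected null in C6 would then be found whether or not MA had changed press-related activation in that way. At stake is what the trial may say about specificity: a null on this contrast could be read as evidence that MA leaves the motor response alone, when the contrast was blind to the most obvious form of such an effect.

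**Working it through.** The plan gives no figure for the motor check, so there is none to reproduce. The check is algebraic, followed by an illustration of size.

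**Inputs from the plan.** Win-minus-loss scoring (imaging data analysis); the same press on all trial types (MID task); MA versus PL within subject on the extracted values (C6, Aim 1); N=160 and alpha .05 (C6).

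**Assumptions not in the plan.** Two-sided paired t test without covariates; SD of each MA-minus-PL difference set to 1; correlation ρ between the win and loss differences of 0, 0.5 or 0.8.

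**Step 1: what is tested.** Let δ_win and δ_loss be the MA-minus-PL effects on the motor-response estimate for each trial type.

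D = (MA_win − MA_loss) − (PL_win − PL_loss) = δ_win − δ_loss

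If δ_win = δ_loss, the expected value of D is 0, whatever the common size. This needs none of the assumptions about SD or ρ.

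**Step 2: the follow-up contrasts.** Win versus neutral tests δ_win − δ_neutral, and loss versus neutral tests δ_loss − δ_neutral. Both also have expectation 0 if the effect is common to neutral trials, which are not exempted from the press.

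**Step 3: size.** The SD of D is √(2(1−ρ)). The SD of the average (δ_win + δ_loss)/2 is √((1+ρ)/2). For a common effect of 0.2, the noncentrality of the test on the average is 0.2 × √160 / √((1+ρ)/2) = 2.530/0.707, 2.530/0.866 and 2.530/0.949, that is 3.58, 2.92 and 2.67. For D it is 0.

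| MA effect in SD (win, loss) | Rejection, win minus loss (ρ = 0 / 0.5 / 0.8) | Rejection, average of win and loss (ρ = 0 / 0.5 / 0.8) |
|---|---|---|
| 0.2, 0.2 | 5 / 5 / 5% | 94 / 83 / 76% |
| 0.5, 0.5 | 5 / 5 / 5% | about 100% |
| 0.94, 0.94 | 5 / 5 / 5% | about 100% |
| 0.5, 0.4 | 14 / 24 / 51% | about 100% |
| 0.5, 0 | 99% or more | 99 / 95 / 91% |

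The values come from the noncentral t distribution. Simulation with 3,000 replicates agreed, giving 4–5% for win minus loss in the common-effect rows. The last two rows show the limit of the point: an effect that differs by valence does not cancel, and a large difference is detected well.

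**The case against.** **The scoring rule may not be meant for motor.** The win-minus-loss sentence appears twice in nearly the same words, which looks like an editing duplicate. The plan describes one map per element without saying that the motor regressor is split by valence, and the collapsed wording would not cancel a common effect. This is fair, and it means the plan conflicts with itself rather than clearly settling on win minus loss. But the sentence stands directly after the motor regions without exception, and C6, Aim 2, also scores MID activation as win minus loss. The text has to be resolved either way.

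**For the reward regions, a matched contrast has a use.** The stated purpose of confirming no drug effect is attached to the reward regions. If cue and feedback are scored win minus loss, an additive motor effect common to both trial types cancels there too, and a win-minus-loss motor contrast checks whether a drug-by-valence effect is present in the motor phase. This stands. It does not cover primary sensorimotor cortex, where C6 expects no motor effect in general. Nor does it cover a proportional change in BOLD gain by a factor g. That would alter a cue contrast by (g−1) × (win − loss), but would leave a motor contrast near zero where the press response is the same on win and loss trials.

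**The trial has other controls.** A reader might infer that the trial has no motor or vascular control. The documents do not support that. Finger tapping is scored by a contrast between tap and rest blocks, which does not cancel a general effect, and the ancillary analyses extend it to reward-related and other areas. Arterial spin labelling addresses blood flow, with a covariate if MA changes it. Exploratory whole-brain comparisons are planned for each component, with no contrast stated. These controls are partial: the tapping regions listed under imaging data analysis are only primary motor cortex, caudate and putamen, block tapping is not the cued speeded press, and blood flow is not motor response.

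**The 5% figure is simply alpha.** True. The numbers only illustrate; the finding is the cancellation.

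**Conclusion.** The point holds in a limited form. On the wording of the imaging data analysis section, the MID motor contrast has only alpha-level rejection against an MA effect common to win and loss trials. A null result there cannot support the C6 expectation of no drug effect on motor, particularly in primary sensorimotor cortex. Separately, the collapsed wording in the MID description and the win-minus-loss rule cannot both govern the motor component.

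A reader might infer that the check would come out null whatever MA does. It would not: only the part of the effect that is equal across win and loss cancels, and a true null is still rejected 5% of the time. Nor does the point show that the striatal findings would be wrong or unsupported. No power figure in the plan rests on this check, and it is one of several controls.

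The cancellation rests only on the text and on the drug effect being equal across trial types, which is plausible for a shared press but is an assumption because incentives differ. The 76–94% range for the averaged contrast at 0.2 SD rests on the assumed SD and correlations.

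**What to change.** In the imaging data analysis section, define MID motor activation for the drug check as the response-locked estimate averaged over all trial types (win, loss and neutral) against baseline. Compare MA with PL on it in each listed region, and report the estimate with a confidence interval, since non-significance alone does not show that an effect is absent. Keep win minus loss for valence questions, with a matched win-minus-loss motor contrast as a secondary analysis if wanted. Reconcile the collapsed wording in the MID task description with the win-minus-loss rule by stating which contrast applies to cue, motor response and feedback.

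The cost is SAP wording and one additional summary from the same imaging data; no new data or scan time is needed.
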